5.4.1.3 Supportive Analyses

A PP analysis will be performed on the primary endpoint if there is greater than or equal to a 10% difference in the number of subjects between the PP and mITT populations.

Primary and secondary endpoints will be analyzed separately for each subgroup.

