Subgroup analyses for primary and secondary endpoints.	Subgroup analyses for 
 sex (male and female) age (18-34 and 35-64 years)
Safety	
To monitor the safety of the study treatment with daily use for 12 weeks.	The number of Treatment-emergent adverse events (TEAEs)

This study will be considered successful if daily use of Emergen-C supplementation improves QoL (as measured by any of the individual domain scores), compared to placebo at Week 12.

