8.3 Statistical Analyses

Additional details of the proposed statistical analysis will be documented in the statistical analysis plan (SAP), which will be written following finalization of the protocol and prior to study unblinding/analysis (as appropriate). This section is a summary of the planned statistical analyses of the primary and key secondary endpoints and a brief summary of how other collected data will be analyzed.

The mITT population will be used for all efficacy analyses.

All p-values presented will be two-sided and assessed at the 5% significance level. A sequential testing strategy will be used to adjust for the comparisons between the Emergen-C and placebo group at each assessment time point.

Change from Baseline in each of the MFI domain scores at earlier timepoints will only be assessed for confirmatory evidence if the change from the later timepoint achieves a statistically significant difference. Each domain will only be evaluated if the change from Baseline to 12 weeks (primary endpoint) was significant at the Bonferroni-Holm adjusted significance level. A significance level of 5% applies to all subsequent analyses of timepoints. This strategy will begin at Week 12, then move to Week 8, then to Week 4. There will be no further adjustments for multiplicity for other secondary endpoints.

Summary Statistics (mean, median, SE, SD, minimum, maximum) will be presented for each outcome variable at each assessment time point. Raw means (+/- SE) of the primary and secondary endpoints will be plotted by treatment group.

The results from each Mixed Model with Repeated Measures (MMRM) will be tabulated, presenting the least square mean change from baseline for each treatment group at each timepoint and the comparison between Emergen-C and Placebo, with two-sided p-values and 95% CIs.

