4.2 Subgroups/Stratifications

The following subgroups will be constructed and analyzed for primary and secondary analyses as an exploratory outcome:

- Sex (male vs. female subjects)
- Age groups (18-34 years vs. 35-64 years).

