5.4.1.2 Statistical Hypothesis, Model, and Method of Analysis

The primary analyses assess the following hypothesis for each MFI domain score:

$$H_0: MFI_{12w-baseline_{Control}} = MFI_{12w-baseline_{Intervention}}$$

$$H_1: MFI_{12w-baseline_{Control}} \neq MFI_{12w-baseline_{Intervention}}$$

Where $MFI_{12w-baseline_{Control}}$ represents the change in MFI domain scores from baseline to 12 weeks in the control group, and $MFI_{12w-baseline_{Intervention}}$ refers to the change in the intervention group.

Change from baseline for each of the MFI domains listed above will be analyzed using a linear mixed-effects model for repeated measures (MMRM) with randomized treatment arm, timepoint as a factor and [treatment x timepoint] interaction as fixed effects, and the respective baseline MFI domain score as a covariate. Subject will be included as a repeated measure with an unstructured covariance matrix. Kenward-Rogers degrees of freedom will be applied (Kenward and Roger 1997). The difference between the least square mean change from baseline for the treatment compared to placebo group at Week 12 from the MMRM will be presented along with the two-sided p-value and 95% confidence interval (CI).

Using the above model, the adjusted mean change from baseline in MFI domains will also be reported by study product along with the 95% confidence intervals (CIs) and p-values testing for a non-zero change from baseline.

A significance level of 5% is used to evaluate the primary endpoint. To account for multiple comparisons, a Bonferroni-Holm correction will be applied to the p-values and CIs of the mean change between groups for the MFI domain scores at week 12. Change from Baseline in each of the MFI domain scores at earlier timepoints will only be assessed for confirmatory evidence if the change from the later timepoint achieves a statistically significant difference. Each domain will only be evaluated if the change from Baseline to 12 weeks (primary endpoint) was significant at the Bonferroni-Holm adjusted significance level. A significance level of 5% applies to all subsequent analyses of timepoints. This strategy will begin at Week 12, then move to Week 8, then to Week 4. There will be no further adjustments for multiplicity for other secondary endpoints. Both adjusted and non-adjusted p-values will be reported (where applicable).

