14.2 Efficacy Data Summary Tables and Figures					
	Table	Summary of Product Compliance	mITT Population	14.2.1.1.1	---
	Table	Summary of MFI Domain Scores	mITT Population	14.2.2.1.1	Yes
	Table	Summary of MFI Individual Item Scores	mITT Population	14.2.3.1.1	Yes
	Table	Summary of Quality of Life (QoL) Questions (Secondary Endpoint)	mITT Population	14.2.4.1.1	
	Table	Summary of Quality of Life (QoL) Questions (Exploratory Endpoint)	mITT Population	14.2.5.1.1	
	Table	Summary of MFI Domain Scores – Sex Subgroup	mITT Population	14.2.2.1.3	
	Table	Summary of MFI Individual Item Scores– Sex Subgroup	mITT Population	14.2.3.1.3	
	Table	Summary of QoL Questions (Secondary Endpoint) – Sex Subgroup	mITT Population	14.2.4.1.3	
	Table	Summary of MFI Domain Scores – Age Subgroup	mITT Population	14.2.2.1.5	
	Table	Summary of MFI Individual Item Scores– Age Subgroup	mITT Population	14.2.3.1.5	

Haleon Confidential

CCI Statistical Analysis Plan template v7.0

CSR Section	TLF	Title	Population	Template	Topline
	Table	Summary of QoL Questions (Secondary Endpoint) – Age Subgroup	mITT Population	14.2.4.1.5	
	Table	Statistical Analysis of Change from Baseline in Multidimensional Fatigue Inventory (MFI) Domains Over Time (MMRM)	mITT Population	14.2.2.1.2	Yes
	Table	Statistical Analysis of Change from Baseline in MFI Individual Item Scores Over Time (MMRM)	mITT Population	14.2.3.1.2	Yes
	Table	Statistical Analysis of Change from Baseline in Quality of Life (QoL) Questions (Secondary Endpoint) Over Time (MMRM)	mITT Population	14.2.4.1.2	
	Table	Statistical Analysis of Change from Baseline in Quality of Life (QoL) Questions (Exploratory Endpoint) Over Time (MMRM)	mITT Population	14.2.5.1.2	
	Table	Statistical Analysis of Change from Baseline in Multidimensional Fatigue Inventory (MFI) Domains Over Time (MMRM) – Sex Subgroup	mITT Population	14.2.2.1.4	
	Table	Statistical Analysis of Change from Baseline in MFI Individual Item Scores Over Time (MMRM) – Sex Subgroup	mITT Population	14.2.3.1.4	
	Table	Statistical Analysis of Change from Baseline in Quality of Life (QoL) Questions (Secondary Endpoint) Over Time (MMRM) – Sex Subgroup	mITT Population	14.2.4.1.4	
	Table	Statistical Analysis of Change from Baseline in Multidimensional Fatigue Inventory (MFI) Domains Over Time (MMRM) – Age Subgroup	mITT Population	14.2.2.1.6	
	Table	Statistical Analysis of Change from Baseline in MFI Individual Item Scores Over Time (MMRM) – Age Subgroup	mITT Population	14.2.3.1.6	

Haleon Confidential

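### The exploratory sex and age analyses are separate fits with no planned estimate of how the treatment effect differs between levels, so discordant within-level p-values could be misread

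*SAP*

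**What the plan says.** SAP 4.2 sets out sex and age group (18-34, 35-64) as follows: "The following subgroups will be constructed and analyzed for primary and secondary analyses as an exploratory outcome". Protocol 8.3.5 gives them the same exploratory status and names no method. The method appears in SAP 5.4.1.3: "Primary and secondary endpoints will be analyzed separately for each subgroup".

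The model is in SAP 5.4.1.2 and, in the same form, Protocol 8.3.1. It has treatment, "timepoint as a factor and [treatment x timepoint] interaction as fixed effects", and the baseline score as covariate. The only interaction is with time, and no subgroup term appears. The Week 12 treatment difference is reported with a two-sided p-value and a 95% CI.

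SAP Appendix 1 lists one domain MMRM table per factor: "Statistical Analysis of Change from Baseline in Multidimensional Fatigue Inventory (MFI) Domains Over Time (MMRM) – Sex Subgroup" (14.2.2.1.4) and "Statistical Analysis of Change from Baseline in Multidimensional Fatigue Inventory (MFI) Domains Over Time (MMRM) – Age Subgroup" (14.2.2.1.6). No title names a between-level contrast, an interaction or a forest plot. SAP section 6, on changes from the protocol, adds none.

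On significance levels, Protocol 8.3 states: "All p-values presented will be two-sided and assessed at the 5% significance level". SAP 5.4.1.2 says that "a Bonferroni-Holm correction will be applied to the p-values and CIs of the mean change between groups" for the domain scores at Week 12.

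**The concern.** A subgroup analysis invites the question of whether the effect differs by sex or by age. The introduction to the protocol encourages it, because one of the supplement studies tabulated in section 1.1 is reported as finding different effects in men and women. Two separate fits give two treatment effects and two p-values. They do not give the difference between the effects or its uncertainty.

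Finding significance in one level and not in the other does not test that difference. Each level has fewer subjects than the whole trial, so one level can easily miss 5% when the true effect is identical in both. A sentence such as 'it works in women but not in men' could then be drawn from chance and unequal subgroup sizes. Protocol 1.1 says the findings are to be communicated to consumers and healthcare professionals, so the wording drawn from these tables matters. Only the reading of the subgroup tables is at stake.

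**Working it through.** **Inputs from the documents.** 120 evaluable per arm, planning effect 0.5 SD, and a two-sided 1% level for sizing (Protocol 4.1). Two-sided 5% for presented p-values (Protocol 8.3). Five domains and two subgroup factors.

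**Assumptions, not in the documents.** Subgroup splits from 50:50 to 75:25, balanced across arms; the same true effect in both levels; an unadjusted two-sample t-test standing in for the MMRM.

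**1. The plan's own figure.** With 120 per arm, 0.5 SD and two-sided 1%, power is 90.3% by the normal approximation and 89.8% by the noncentral t. The stated figure of over 90% is reproduced to within rounding.

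**2. Power within a level.** With a share f of subjects in the larger level, the per-arm sizes are 120f and 120(1 - f). Noncentral t, alpha 5%, common effect 0.5 SD:

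| f | per arm | power, larger level | power, smaller level |
|---|---|---|---|
| 0.50 | 60 / 60 | 0.775 | 0.775 |
| 0.60 | 72 / 48 | 0.846 | 0.679 |
| 0.70 | 84 / 36 | 0.896 | 0.553 |
| 0.75 | 90 / 30 | 0.916 | 0.478 |

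**3. Chance that exactly one level is significant.** The levels contain different subjects, so P = p1(1 - p2) + p2(1 - p1). At f = 0.50: 2 x 0.775 x 0.225 = 0.349 (0.348 unrounded). At f = 0.75: 0.916 x 0.522 + 0.478 x 0.084 = 0.518. Per domain and factor at Week 12:

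| common true effect | f = 0.50 to 0.75 |
|---|---|
| none | 2 x 0.05 x 0.95 = 9.5% |
| 0.2 SD | 31-32% |
| 0.3 SD | 47-51% |
| 0.4 SD | 49-59% |
| 0.5 SD | 35-52% |

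**4. Sensitivity to baseline adjustment.** If baseline correlates r with outcome (assumed), adjustment shrinks the residual SD to sqrt(1 - r^2). At r = 0.5 this is 0.866, and 0.5 SD becomes 0.5 / 0.866 = 0.577 residual SD. Power is then 0.880 in both levels at f = 0.50, and 0.971 and 0.594 at f = 0.75. Discordance is 2 x 0.880 x 0.120 = 21%, and 0.971 x 0.406 + 0.594 x 0.029 = 41%. At r = 0.7 it is 6-24%. With no effect it stays at 9.5%.

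**5. Expected number of discordant pairs.** There are 5 domains x 2 factors = 10 pairs. With no effect, 10 x 0.095 = 0.95 are expected. At a common 0.5 SD in every domain the figure is 10 x 0.348 to 10 x 0.518, or 3.5 to 5.2 unadjusted, and about 2.1 to 4.1 if r = 0.5. In all these cases the true difference between levels is zero.

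**6. What a direct contrast would give.** The difference is d1 - d2, with SE = sqrt(2/(120f) + 2/(120(1 - f))). At f = 0.50 this is sqrt(2/60 + 2/60) = 0.258 SD, and at f = 0.75 it is sqrt(2/90 + 2/30) = 0.298 SD. The 95% CI half-width is 1.96 x SE = 0.51 and 0.58 SD. Power for a between-level difference of 0.5 SD (noncentral t, 236 df) is 49% and 39%. In simulation of the contrast from two separate estimates (40,000 runs, Satterthwaite df, common effects of 0, 0.3 and 0.5 SD), the false-positive rate was 4.8-5.3%.

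**The case against.** The strongest case on the other side is that nothing promised is left undone. Both documents call the subgroup analyses exploratory, state no hypothesis of effect modification and tie no claim to a subgroup. Neither proposes to compare p-values across levels. If the treatment differences and 95% CIs of SAP 5.4.1.2 carry into the subgroup tables, a reader can form the difference with simple arithmetic. Appendix 1 gives titles and no table layouts, so absence from the displays is inferred. The contrasts would also be weak, and a non-significant one could be misread as showing equal effects.

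Much of this stands, and it sets the weight of the point: this is a cheap improvement to exploratory output and corrects no error in the primary analysis. It does not remove the point. The SAP says the fits are separate, and no text or title in either document plans the comparison. A difference that is easy to derive is also easy to print. The risk of misreading a weak contrast can be met with an interval and one sentence of interpretation.

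The size is also sensitive to assumptions. The 35-52% at the planning effect depends on an unadjusted test, as step 4 shows, and should not be quoted without the adjusted range.

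A reader might further infer that the plan leaves the within-subgroup significance level open, or contradicts itself on it. The documents do not support that. Protocol 8.3 assesses all presented p-values at 5%, and SAP 5.4.1.2 confines the Bonferroni-Holm step to the Week 12 domain scores. Nominal 5% is the natural reading for the subgroup fits. At most, a line confirming it would help.

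**Conclusion.** The point holds as one to consider. The plan provides no direct estimate of whether the treatment effect differs by sex or by age, and side-by-side p-values are a poor substitute. With identical true effects in both levels, 120 evaluable per arm, splits of 50:50 to 75:25 and nominal 5%, a discordant pair arises in 9.5% of cases with no effect and in roughly a third to three fifths at effects of 0.2 to 0.5 SD, before baseline adjustment. At 0.5 SD the range is about 21-41% if baseline correlates 0.5 with outcome. The splits, the common effects and the correlation are all assumed; the 0.5 SD is the plan's own design effect.

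A reader might infer that the trial's main result is weakened, or that the sponsor intends to claim a sex or age effect from separate p-values. Neither follows. Protocol section 2 defines success on the overall Week 12 domain comparisons, and no subgroup result enters that criterion.

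**What to change.** Keep the planned separate fits. For the five MFI domains at Week 12, add to the sex and age MMRM tables (14.2.2.1.4 and 14.2.2.1.6) the between-level difference in treatment effect with its 95% CI: d1 - d2, SE = sqrt(SE1^2 + SE2^2), Satterthwaite degrees of freedom. A p-value is optional. Add a note to the tables stating that:

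- the contrasts are exploratory and unadjusted for multiplicity;
- within-subgroup p-values are not evidence of effect modification;
- a non-significant contrast is not evidence of equal effects.

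The cost is a short SAP change and 10 result lines computed from estimates already produced, with no new data, model or sample size. If the treatment codes have already been opened, the contrasts should be labelled post hoc.

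There are two downsides. The contrasts are imprecise: by step 6 most will be inconclusive and should be reported as such. If they are tested at 5%, 10 x 0.05 = 0.5 false positives are expected when no effect differs, and the chance of at least one would be 1 - 0.95^10 = 40% if they were independent. For that reason the addition should stay with the domains at Week 12 and not extend to the single items and QoL questions.

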5.4.2 Handling of Missing Values

MMRM analyses account for missing data using ‘a missing at random’ assumption, i.e., there is a systematic relationship between the propensity for missing values and the observed data, but not the missing data. Under such assumptions, MMRM is shown to provide unbiased estimates of the treatment effect whilst analysis of only complete cases using analysis of covariance (ANCOVA) is biased (Ashbeck and Bell 2016; Baron et al. 2008).

Such complete case analysis requires a ‘missing completely at random’ assumption to remain unbiased and this is unlikely to hold, i.e., the fact that the data are missing is independent of the observed and unobserved data.

Using an MMRM, it will therefore be assumed that a subject with missing data at one post-baseline assessment visit would have obtained a similar efficacy result at that visit compared to a subject using the same investigational product with similar non-missing results at other timepoints (baseline and the other post-baseline assessment visits).

5.5 Analysis of Secondary Objectives

5.5.1 Efficacy (Secondary)

The secondary endpoints of each MFI domain at week 4 and week 8 will be summarized descriptively and analyzed as described for the primary endpoint. Non-adjusted *p*-values and 95%-CIs will be reported, which need to be interpreted in light of the results of the primary endpoint.

Similarly, the secondary endpoint for each of the individual MFI questions will be summarized descriptively and analyzed as described for the primary endpoint, but with baseline of the MFI domain score replaced with the individual MFI question score at baseline for the respective MFI item for each timepoint (week 4, week 8 and week 12).

The secondary endpoint for each of the supplementary quality of life (QoL) questions will also be summarized descriptively and analyzed using the same MMRM model described above, but with baseline of the MFI domain score replaced with the baseline of the respective quality of life question for each timepoint (week 4, week 8 and week 12).

5.6 Exploratory Analyses

The number of days reported at each timepoint for the previous 4 weeks (and total) will be listed and summarized by treatment group in the mITT population using descriptive statistics for:

- days feeling rundown
- days canceling plans
- days with cough and flu symptoms
- days of work missed

The exploratory endpoint for each of the supplementary quality of life (QoL) questions will also be summarized descriptively and analyzed using the same MMRM model described above, but with baseline of the MFI domain score replaced with the baseline of the respective quality of life question for each timepoint (week 4, week 8 and week 12).

5.7 Analysis of Safety

5.7.1 Adverse Events and Serious Adverse Events

The absolute and relative frequency of adverse events (AEs) in each group will be reported, including the total number of events, the total number of patients experiencing at least one event, and the frequency of events by severity and AE category. Safety analyses will be performed on the Safety population, according to investigational product received. AEs will be regarded as ‘treatment emergent’ if they occur on or after the first use of investigational product at baseline (visit 2). In the event of a missing start date, an AE will be assumed to be ‘treatment emergent’ unless the end date is prior to starting treatment. In case of misallocation compared to the randomization schedule, TEAEs will be associated with the most recent investigational product received.

A listing of all AEs will be presented for all subjects in the Safety population with the following AE summaries (number of distinct AEs and frequency/proportion of subjects affected) presented by treatment group and overall:

- TEAEs
- TEAEs by System Organ Class (SOC) and Preferred Term (PT)
- Treatment emergent treatment related AEs by SOC and PT
- Treatment emergent treatment related serious AEs by SOC and PT

Separate listings will be presented for:

- Deaths, Severe AEs (SAE) and any AEs leading to product or study discontinuation.
- Exposure to study product

Haleon Confidential

CCI Statistical Analysis Plan template v7.0

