5.1 Schedule of Activities

The Schedule of Activities (Table 5-1) provides an overview of the subjects virtual visits, study procedures and assessments. The investigator may schedule additional (unplanned) virtual visits to conduct additional evaluations or assessments required to protect the well-being of the subject. A detailed schematic of the Schedule of Activities is located in section 9.9 Schedule of Activities Schematic.

Table 5-1 Schedule of Activities

Visit	Treatment Period					
	Pre-screening	Visit 1 Screening & Baseline	Treatment Initiation	Virtual Visit 2	Virtual Visit 3	Virtual Visit 4
Study Day	Day-7 to Day -2	Day -7 to Day -2	Day 1	Week 4 Day 28 (+5)	Week 8 Day 56 (+5)	Week 12 Day 84 (+5)
Medical/Medication History ^a	X					
Demographics ^a	X					
Informed Consent	X					
Subject ID Verification		X				
Inclusions/Exclusion Criteria ^c		X				
Eligibility Assessment		X				
MFI ^a	X			X	X	X
Supplementary QOL questionnaire ^a		X		X	X	X
Randomization		X				
Participant Training		X				
Study Product Shipped		X				
Concomitant Medication Check		X		X	X	X
Adverse Event (AE/ Serious Adverse Event)		X	X	X	X	X
Study Product Administration ^b			X (Daily through Week 12 visit)			
Participant Daily eDiary ^d			X (Daily through Week 12 visit)			
Subject Conclusion/Subject Exit from Study						X
Exit Survey ^a						X

Footnotes:

^aSubject-reported (self-reported) assessments.

Property of Haleon- Confidential

May not be used, divulged, published or otherwise disclosed without the consent of Haleon

CCI [REDACTED] Abbreviated Clinical Protocol Template v1.0

^bSubject will take the study product in the morning of each day

^cSubject will self-report pregnancy status during Visit 1

^dSubject-reported (self-reported) they took the investigational product on that day.

The virtual site may contact subjects prior to study visits, either as part of pre-screening activities or as a reminder of the approaching scheduled visit. Further details should be included in the electronic informed consent (eICF).

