 - Once the shipment is successfully received, the subject will confirm receipt via an online questionnaire directly entered into the EDC platform.
 - If unsuccessful (e.g. lost, damaged) study team will discuss with participant and arrange a new shipment if needed

Following the completion of the screening visit, and prior to Virtual Visit 2, subjects will be reminded each morning to consume the study product with 4-6 ounces of water at approximately the same time each day. Each evening, subjects will be prompted to complete an Electronic Diary (eDiary) consisting of one question to confirm the subject has consumed the study product.

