8.3.4 Safety Analysis(es)

The absolute and relative frequency of AEs in each group will be reported, including the total number of events, the total number of patients experiencing at least one event, and the frequency of events by severity and AE category.

Safety analyses will be performed on the Safety population, according to investigational product received. AEs will be regarded as 'treatment emergent' if they occur on or after the first use of investigational product at Baseline (Visit 2). In the event of a missing start date, an AE will be assumed to be 'treatment emergent' unless the end date is prior to starting treatment. In case of misallocation compared to the randomization schedule, TEAEs will be associated with the most recent investigational product received.

AE will be assessed by the investigator or medically qualified designee. AE review and coding will be in line with the Site and Safety Management Plan.

A listing of all AEs will be presented for all subjects in the Safety population with the following AE summaries (number of distinct AEs and frequency/proportion of subjects affected) presented by treatment group and overall:

- TEAEs
- TEAEs by System Organ Class (SOC) and Preferred Term (PT)
- Treatment emergent treatment related AEs by SOC and PT
- Treatment emergent treatment related serious AEs by SOC and PT

Separate listings will be presented for:

- Deaths, SAEs and any AEs leading to product or study discontinuation.
- Exposure to study product

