9.1.3 Time Period and Frequency for Collecting AE and SAE Information

All AEs, and therefore all SAEs (except from those exempt from recording, as described in section 9.1.1 and section 9.1.2) will be collected from immediately after a subject is randomised within the trial and until 2 days following the last administration of study product (or the last study procedure).

Medical occurrences that began before randomisation will be recorded in the Medical History/Current Medical Conditions section of the Electronic Case Report Form (eCRF), not the AE section.

Details recorded by the subject that meet the definition of a serious AE must be discussed with the subjects and transcribed into the SAE section of the eCRF.

All SAEs will be recorded and reported to the sponsor or designee immediately, and under no circumstance should this exceed 24 hours. The investigator will submit updated SAE data to the sponsor within 24 hours of it being available.

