5.1.3 Analysis Populations

Three analysis populations are defined.

Population	Definition / Criteria	Analyses Evaluated
Safety	
 • Comprise of all subjects who receive at least one dose of study product. • This population will be based on the treatment the subject actually received. 	
 • Safety
Modified Intent-To-Treat (mITT)	
 • Comprise of all randomized subjects with completed baseline visit (visit 1), at least one completed post-baseline MFI domain assessment, and taken at least one dose of allocated product. • This population will be based on the treatment to which the subject was randomized. 	
 • Demographics • Baseline Characteristics • Efficacy • Subgroup analyses

Population	Definition / Criteria	Analyses Evaluated
	
 Any subject who receives a randomization number will be considered to have been randomized. 	
Per-Protocol (PP)	
 Comprised of all subjects in the mITT population who have adhered to treatment regime and were not affected by protocol deviations. 	
 Sensitivity (Primary endpoint)

Note: Please refer to [Appendix 1](#): List of Data Displays which details the population to be used for each display being generated.

The numbers of subjects included in each of the analysis populations will be summarized (Table 14.1.1). Subjects excluded from any of the analysis populations will be listed in Listing 16.2.3.1, with the reason for exclusion.

The primary population for assessment of efficacy will be the mITT Population. A PP analysis will be performed for efficacy analysis of the primary endpoint if at least 10% of the mITT subjects are excluded from the PP Population. Efficacy data determined to have been potentially impacted by a protocol deviation will be excluded from the PP analysis. A decision on whether a protocol deviation impacts efficacy data and whether to perform a PP analysis will be made at the BDRM.

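### Does the visit label in the treatment-emergent definition drop the first four weeks of adverse events?

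*SAP*

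**What the plan says.** Both documents define a treatment-emergent adverse event (TEAE) by the first use of product and then attach a visit label. SAP 5.7.1 applies the definition to events "if they occur on or after the first use of investigational product at baseline (visit 2"). Protocol 8.3.4 says "if they occur on or after the first use of investigational product at Baseline (Visit 2").

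The label conflicts with the rest of the plan:

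- The schedule in Protocol 5.1 heads the baseline column "Visit 1 Screening & Baseline", at Day -7 to Day -2. The SAP schedule (section 4.3) agrees.
- The modified intention-to-treat definition in SAP 5.1.3 requires a "completed baseline visit (visit 1"). Protocol 8.2.1 also calls baseline visit 1.
- Both schedules give treatment initiation its own column at Day 1, with no visit number, and put Virtual Visit 2 at Week 4, Day 28 (+5).

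In the same SAP section, the bullet for separate listings reads "Deaths, Severe AEs (SAE) and any AEs leading to product or study discontinuation".

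**The concern.** Taken word by word, the definition points to three dates: the first dose (Day 1), the baseline visit (2 to 7 days earlier) and Visit 2 (Week 4). The choice would matter. The number of TEAEs is the only safety endpoint in Protocol Table 2-1, and the three adverse event summary tables in SAP Appendix 1 (14.3.1.1 to 14.3.1.3) are all limited to treatment-emergent events. Pre-dose events can also be in the data, because Protocol 9.1.3 says events "will be collected from immediately after a subject is randomised within the trial and until 2 days following the last administration of study product", and randomisation comes before the product is shipped.

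A window that opened at Visit 2 would leave about the first four weeks of dosing out of the summaries, in both arms. A window that opened at the baseline visit would count events that occurred before any dose.

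The expansion of SAE as severe raises a similar worry. Protocol 9.1.7 warns against confusing severity with seriousness, and a listing selected on severity would miss serious events rated mild or moderate.

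**Working it through.** The plan states no figure to reproduce here. The check compares the possible anchors and counts the days each would misclassify.

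**Inputs.** First dose: Day 1 (both schedules). Visit 2: Day 28 to Day 33. Week 12 visit: Day 84 to Day 89. Baseline visit: Day -7 to Day -2.

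**Anchor 1, first use.** The window opens on Day 1. Treatment days outside it: 0. Pre-dose days inside it: 0.

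**Anchor 2, the Visit 2 date.** Days lost = Visit 2 day - 1. Share lost = days lost / last treatment day.

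| Visit 2 on | Days lost | Share of 84 days | Share of 89 days |
|---|---|---|---|
| Day 28 | 28 - 1 = 27 | 27/84 = 32.1% | 27/89 = 30.3% |
| Day 33 | 33 - 1 = 32 | 32/84 = 38.1% | 32/89 = 36.0% |

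These are shares of time. They become shares of events only if the event rate is constant over treatment, which is an assumption; the documents give no rate.

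**Anchor 3, the baseline visit.** Pre-dose days included: 2 to 7, counting Day -1 as the day before Day 1.

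**Which anchor the text selects.**

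1. The condition is that the event falls on or after the first use of product. Each subject has one first use, so the visit label only misdescribes where it happens.
2. First use cannot be at Visit 2. Protocol 5.4 states: "Following the completion of the screening visit, and prior to Virtual Visit 2, subjects will be reminded each morning to consume the study product".
3. It cannot be at the baseline visit either. Product is shipped after Visit 1, and SAP 4.1 defines the baseline value as a pre-dose assessment.
4. The next sentence of SAP 5.7.1, on missing start dates, treats an event as treatment emergent "unless the end date is prior to starting treatment". Its reference point is the start of treatment, with no visit attached.
5. SAP 5.3.2 separates prior from concomitant medication at the first use of product, again with no visit number.
6. The date is available. SAP 5.1.1 lists study product start date and time, and the dose counts in SAP 5.3.1 run from treatment initiation.

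Anchor 1 is the only one that satisfies the stated condition. Anchor 2 requires the analyst to disregard both first use and baseline and keep only the parenthesis. Anchor 3 counts events that precede first use, which the condition excludes.

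**The serious/severe slip.** The heading of SAP 5.7.1 and its last summary bullet say serious. In Appendix 1, Table 14.3.1.3 covers serious events, and Listing 14.3.2.2 covers non-fatal serious events. No display selected on severity is planned in its place.

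**The case for a change.** The best argument for a change is that the definition of the only safety endpoint should not depend on the reader ignoring part of it. The error appears in both documents, so comparing one with the other does not expose it. No table of all adverse events is listed in Appendix 1 as a backstop. A Visit 2 cut-off would also reach beyond the tables: Listing 14.3.2.3 is restricted to treatment-emergent events that led to discontinuation, so early discontinuations would drop out of it too.

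The label is indeed wrong, and the wider reach of a Visit 2 cut-off is correctly described. But each consequence depends on a derivation that contradicts the rule's own trigger, the sentence after it and the dosing schedule. Even then the events would remain in the report: SAP 5.7.1 calls for a listing of all adverse events in the Safety population, and Listing 16.2.7.1 covers all events in all randomised subjects. Events with a missing start date would be kept unless they ended before treatment.

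Correcting the protocol text would also have a cost, since Protocol 9.6.1 requires ethics approval of amendments.

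**Conclusion.** The concern does not hold as a fault in the analysis. The visit label in Protocol 8.3.4 and SAP 5.7.1 is a clerical error, and so is the expansion of SAE as severe. Under the trigger as written, 0 treatment days are lost and no pre-dose events are counted. The 27 to 32 days (30% to 38% of an 84- to 89-day period) measure a programming mistake that the text does not direct.

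This rests on two assumptions: that the recorded product start date is used to open the window, as the rule's trigger and the neighbouring sections indicate, and that the serious-event listing follows Appendix 1. On both points an analyst working from the SAP has enough to reach the intended result. Tidying the wording when the SAP is next edited would be harmless, but it would change no table, listing or conclusion.
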